7.8 Stratification Factors and Subgroups

There are no stratification factors or subgroups for this trial.

7.9 Standard Calculations

7.9.1 Age

Age will be calculated as the number of completed years between the date of informed consent and the subject's birth date.

Age (years) = integer of [(date of informed consent – date of birth)/
$$365.25$$
]

7.9.2 Change from Baseline

Change will be calculated using post baseline data and baseline data according to the formula noted below.

7.9.3 Time to event

Time to event will be calculated according to the formula noted below:

Time to event = (Date of Event
$$-$$
 Date of first treatment) + 1

8. STATISTICAL METHODS

All data from this clinical trial will be provided in data listings, study drug, clinical trial center, subject, and time point (if applicable).

Data summary will be according to the variable type:

- Continuous data summaries will include:
 - Number of observations, mean, standard deviation, median, and minimum and maximum values.

- Categorical data summaries will include:
 - o Frequency counts and percentages.

8.1 Summarizing and Tabulating the Collected Data

8.1.1 Subject Disposition and Withdrawals

There will be a detailed accounting of all subjects who sign an informed consent to participate in this study. The following will be summarized:

- The number of subjects who are signed informed consent
- The number of subjects received treatment in phase Ib
- The number of subjects received treatment in phase II
- The number of subjects who completed treatment in phase Ib
- The number of subjects who completed treatment in phase II
- The number of subjects who discontinued prior to completion
 - Reasons for discontinuation prior to completion will also be summarized descriptively

In addition, there will also be a listing of all discontinued subjects, which will provide the clinical trial center and the specific reason for discontinuation.

8.1.2 Protocol Deviations

The major protocol deviations occurred during the clinical trial will be summarized descriptively according to the following categories:

- Informed consent not properly attained
- Developed withdrawal criteria during the study but not withdrawn
- Received excluded concomitant medication
- Did not meet Inclusion/ Exclusion criteria but entered into the study

Additionally a by-subject listing of all deviations will also be prepared.

8.1.3 Demographics and Other Baseline Characteristics

Demographics (age, race, gender, ethnicity), height, weight will be listed and summarized descriptively. See Section 7.1 for baseline definition.

Medical history findings will be provided as by-subject listings.

8.1.4 Prior and Concomitant Medications

All prior and concomitant medications recorded in the case report form will be using the most recent version of WHO Drug dictionary. Descriptive summaries will be prepared using the coded Protocol: CD07_TNBC CytoDyn, Inc.

term. All prior and concomitant medications recorded in the case report form will be listed and summarized.

8.1.5 Study Drug Administration

All available study drug administration data will be listed and summarized.

8.2 Analysis Primary Outcome Measure

8.2.1 Maximum Tolerated Dose (MTD) by evaluation of dose-limiting toxicities (DLTs) of leronlimab (PRO 140) when combined with carboplatin AUC5

The MTD will be summarized descriptively. The proportion of subjects at the different MTD levels and those who were able to tolerate the highest dose of leronlimab will be summarized descriptively.

8.2.2 Progression free survival (PFS) defined as time in months from the date of first study treatment to the date of disease progression or death from any cause, whichever comes first.

PFS will be calculated from the date of initial dose to the date of objective disease progression or death due to any cause, whichever occurs earlier. If patients discontinued treatment due to toxicity, withdrew consent without disease progression or death, PFS will be censored at the date of the last evaluable tumor assessment. A patient with no evaluable tumor assessments or who drop out before first follow-up period will be censored at the date of informed consent. If two or more consecutively scheduled tumor assessments have no data (not evaluable due to incomplete assessment, not assessed, or missing) and are followed by a PD assessment or death, the PFS will be censored at the last evaluable tumor assessment date prior to the assessments with no data. Patients will be explicitly censored for PFS at last adequate tumor assessment prior to initiation of new anticancer treatment or radiation.

Patients who are off-treatment without objective PD and getting the subsequent new anticancer therapy before the data cut-off then PFS will be censored at the last adequate tumor assessment before the new anticancer treatment start, regardless of whether there was a PD or death after the start of the new anticancer treatment.

Progression free survival (PFS) will be estimated using Kaplan-Meier curves, and the median PFS will be read from this curve.

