2.4 Outcome Measures

2.4.1 Primary Outcome Measure

Phase Ib

 Maximum Tolerated Dose (MTD) by evaluation of dose-limiting toxicities (DLTs) of leronlimab (PRO 140) when combined with carboplatin AUC5.

Note: The MTD is defined as 1 dose level below the dose in which dose limiting toxicities (DLTs) were observed in $\geq 33\%$ of the participants during Cycle 1.

Phase II

• Progression free survival (PFS) defined as time in months from the date of first study treatment to the date of disease progression or death from any cause, whichever comes first.

Note: All patients who receive at least one dose of leronlimab (PRO 140) and carboplatin combination will be included in the primary analyses of PFS. The Response Evaluation Criteria in Solid Tumors (RECIST v1.1) criteria will be used for objective tumor response assessment (when disease is measurable and non-measurable);

The time in months from start of treatment to progression or death will be measured for all patients who receive at least one dose of study drug. Patients will be followed up to 2 years after completion of treatment.

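### SAP 8.2.2 censors some patients at informed consent, before PFS starts, and leaves unclear how early deaths and toxicity stops are handled

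*SAP*

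**What the plan says.** - **Origin and event.** SAP 8.2.2 opens: "PFS will be calculated from the date of initial dose to the date of objective disease progression or death due to any cause". SAP 2.4.1 agrees, defining PFS as "time in months from the date of first study treatment to the date of disease progression or death from any cause", and adds: "All patients who receive at least one dose of leronlimab (PRO 140) and carboplatin combination will be included in the primary analyses of PFS".
- **No assessment or early drop-out.** "A patient with no evaluable tumor assessments or who drop out before first follow-up period will be censored at the date of informed consent".
- **Toxicity and withdrawal of consent.** "If patients discontinued treatment due to toxicity, withdrew consent without disease progression or death, PFS will be censored" at the last evaluable tumor assessment.
- **Missed scans.** "If two or more consecutively scheduled tumor assessments have no data" and progression or death follows, "the PFS will be censored at the last evaluable tumor assessment date prior to the assessments with no data".
- **New anticancer therapy.** Censoring is at the last adequate assessment before it starts, "regardless of whether there was a PD or death after the start of the new anticancer treatment".
- **Time formula.** SAP 7.9.3 takes the event date minus the date of first treatment, plus 1.
- **Consent.** SAP 2.1 has a separate pre-screening consent and then a screening consent. Screening assessments, including imaging, fall within 28 days of first treatment. SAP 2.2.2 sets no window for pre-screening.
- **After a toxicity stop.** SAP Appendix 1, footnote 22, and protocol 4.4 continue imaging every 9 weeks until progression and use that progression time in the analysis.
- **Sensitivity analysis.** SAP 7.4 plans none.

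**The concern.** There are four problems in one paragraph.

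1. **The censoring date precedes the origin.** The resulting time is zero or negative, and a negative time cannot enter a Kaplan-Meier risk set. The SAP does not say which of the two consents applies. The other rules in 8.2.2 share the gap: if the only assessment is the baseline scan, they also censor before first dose.
2. **The trigger is unclear.** ITT patients must have measurable disease at baseline (SAP 6.1.1), so a patient with no evaluable assessment at all cannot literally exist. The word post-baseline is missing. The first follow-up period is undefined, and the only Follow-Up Period described in SAP 2.1 comes after treatment. On that meaning, the sentence would send a patient who withdraws consent on treatment after clear scans back to the consent date, while the sentence before it censors her at her last evaluable scan.
3. **Early death is not addressed.** A patient who dies before the first post-baseline scan is an event under the opening sentence, but can be read as censored under this one.
4. **The toxicity sentence is ambiguous.** It is unclear whether the absence of progression or death is a condition for toxicity stops as well as for consent withdrawal. If not, the sentence discards progressions that footnote 22 says will be used.

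The median will be read beside the reference of about 5 months in SAP 2.1. Censoring early deaths could only raise it or leave it unchanged.

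**Working it through.** The plan gives no power or event calculation to reproduce. SAP 3 rests N = 30 on clinical judgment.

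**Invalid times.** Time = censoring date - first dose + 1.

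| Consent or baseline scan before first dose | Time (days) |
|---|---|
| same day | +1 |
| 1 day | 0 |
| 7 days | -6 |
| 28 days | -27 |
| 42 days (possible for pre-screening consent) | -41 |

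**Event-free patients.** A patient censored at or before Day 1 is not at risk at any later event. In 5,000 simulated trials for each of 1, 2 and 3 such patients, the median was compared under Day 1 censoring, a -27-day time and exclusion. It differed in 0 of 15,000.

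**Early deaths, if censored.** Assume n = 30, exponential PFS and a true median of 5.0 months, so L = ln2/5. Let the k earliest failures be deaths before week 6. Removing them moves the observed median to the quantile q = (k + (30 - k)/2)/30, at time -ln(1 - q)/L.

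- k = 1: q = 15.5/30, 5.24 months
- k = 2: q = 16/30, 5.50 months
- k = 3: q = 16.5/30, 5.76 months

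The middle values depend on the median convention, which the SAP does not state. Taking the first time at which S is 0.5 or less, at the expected quantiles, gives 4.76 with deaths counted and 5.25, 5.25 and 5.76 with them censored.

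**With scan timing.** In 300,000 simulated trials, deaths fall on their exact date and progression is seen at the next scan.

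| Scan grid | k | Deaths counted | Deaths censored | Mean shift (months) | Median unchanged |
|---|---|---|---|---|---|
| SAP 2.1 (weeks 6, 12, 18, then 9-weekly) | 1 | 6.12 | 6.38 | +0.25 | 75% |
| | 2 | 6.10 | 6.62 | +0.52 | 52% |
| | 3 | 6.04 | 6.82 | +0.78 | 52% |
| SAP Appendix 1, footnote 8 (6-weekly to 13 months, then 9-weekly) | 1 | 5.81 | 6.05 | +0.24 | 67% |
| | 2 | 5.78 | 6.28 | +0.50 | 39% |
| | 3 | 5.72 | 6.48 | +0.76 | 39% |

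Shifts were computed before rounding. The censored median was never lower. The standard error is about 5/(ln2 × √30) = 1.32 months.

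**How many early deaths?** The documents give no rate.

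- At an assumed risk of 1%, 2% or 5% before week 6, the chance of at least one in 30 is 1 - (1 - p)^30 = 26%, 45% or 79%.
- The 9 to 12 month median survival in protocol 1.5, if exponential, gives 30 × (1 - 0.5^(1.38/9)) = 3.0 to 30 × (1 - 0.5^(1.38/12)) = 2.3 deaths, with 6 weeks = 1.38 months.
- ECOG 0-1 and a life expectancy of at least 6 months argue for fewer. Admitting patients who failed first-line chemotherapy plus a checkpoint inhibitor argues for more.

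**If the follow-up period meant the post-treatment one.** Let a share p drop out on treatment before an event, so the drop-out hazard is D = L × p/(1 - p). Discarding their clear scans leaves a median of ln2/(L + D) = 5(1 - p), which is 4.5 or 4.0 months for an assumed p of 10% or 20%.

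No figure is offered for the toxicity sentence, because the documents give no stopping rate.

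**The case against.** The strongest reply is that the one clear error does no numerical harm. For event-free patients, Day 1, a negative time and exclusion all give the same median. That stands. The rule still cannot be programmed as written, and SAP 2.4.1 promises to include everyone dosed with the combination.

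Second, the range of 0 to -27 days is conditional. SAP 8.2.2 does not cite 7.9.3, the 28-day limit applies to screening assessments rather than to consent, and same-day consent gives +1. This is fair as to the bound. It does not rescue the rule: any consent before the day of dosing gives zero or less, and pre-screening consent may be earlier still.

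Third, early deaths are probably meant to count. The missed-scan and new-therapy rules say when censoring overrides death and this sentence does not; protocol 5 treats death as completion rather than drop-out. I accept that this is the better reading. The figures above therefore describe what a literal reading would cost, not what the plan will necessarily do. They lie inside one standard error of a descriptive median, in a study with no formal test (SAP 5).

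Fourth, the toxicity sentence can be read to agree with footnote 22. It can, but the SAP should say which reading applies.

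Finally, 8.2.2 has no express rule for patients lost after a clear scan or event-free at data cut-off. That gap exists already, and the change below does not widen it.

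**Conclusion.** The concern holds. Censoring at informed consent contradicts the stated PFS origin and gives zero or negative times unless consent is on the day of dosing. For event-free patients the effect on the median is nil.

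The early-death wording is an ambiguity, not an express instruction to censor. If it were applied literally, the median would rise by about 0.25 to 0.8 months for 1 to 3 early deaths in 30 and could never fall. That size assumes exponential PFS with a 5-month median and an early-death count the documents do not supply. The post-treatment reading of the follow-up period would instead lower the median. The toxicity sentence and footnote 22 must be reconciled.

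This should be fixed because it governs the primary endpoint and no planned sensitivity analysis would reveal the effect. It does not threaten the study.

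**What to change.** Rewrite SAP 8.2.2 as follows.

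- **Trigger.** Replace both limbs of the consent-date sentence with one condition: no evaluable post-baseline tumor assessment.
- **Death.** In these patients, count a death before the second scheduled scan as an event on the date of death, which is consistent with the SAP's own two-missed-assessments rule. If new anticancer therapy or radiation began first, the existing new-therapy rule applies.
- **Otherwise** censor at the date of first dose (Day 1), never at consent or the baseline scan. Use Day 1 also wherever another rule in 8.2.2 would fall back on the baseline scan.
- **Toxicity.** State that the absence of progression or death is a condition for toxicity stops too, so that documented progression or death afterwards is an event, subject to the new-therapy and missed-assessment rules.

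While the paragraph is open, add the censoring date for patients lost after a clear scan or event-free at data cut-off.

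The cost is SAP wording only. Survival follow-up and the 9-weekly scans are already planned, except after withdrawal of consent, when protocol 5.1 permits no follow-up. The reported median may be slightly less favourable.

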2. PROTOCOL DESIGN

2.1 Design Overview

Phase Ib

Phase Ib is a dose escalation phase with 3 dose levels (cohorts) of leronlimab (PRO 140) administered in combination with a fixed dose of carboplatin at AUC 5. This dose finding portion of study will follow a "3+3" designed to determine the maximum tolerated dose (MTD) of leronlimab (PRO 140) administered as subcutaneous injection in subjects with histologically confirmed mTNBC that express CCR5. The MTD is defined as 1 dose level (cohort) below the dose in which dose limiting toxicities (DLTs) were observed in ≥ 33% of the participants.

A schematic of the "3 + 3" Dose Escalation Study Design is provided in Appendix 2.

Cohorts of 3 patients are entered at given dose level K. If no patients have a DLT, then the dose will be escalated to the next dose level, K+1. If more than 1 subject has a DLT then the previous dose level, K-1, will be considered as MTD. If 1 subject has a DLT an additional 3 patients will be treated at this dose level, K. If no further subjects suffer a DLT then the dose level will be escalated to K+1 and if any further subjects have a DLT then the previous dose level, K-1, will be considered the MTD. The MTD will be the maximum dose level with an observed toxicity rate of 0% or 17%. If any of the SAEs or DLTs outlined above have occurred, the Data Safety Monitoring Board (DSMB) will conduct an independent review of the data and make a final decision for dose escalation to the next cohort.

The final decision on the MTD will be made following a review of the study data by the DSMB. Continuation into Phase II of the study will take place after the DSMB meeting.

Once the MTD has been determined, subjects enrolled in lower dose cohorts will be allowed to escalate the dose to the MTD, if acceptable per the Investigator's discretion.

Phase II

Phase II is a single arm study with 30 patients in order to test the hypothesis that the combination of carboplatin AUC 5 intravenously and MTD of leronlimab (PRO 140) SC will increase PFS in patients with CCR5 + mTNBC. PFS in patients with newly recurred TNBC is approximately 5 months.

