3. SAMPLE SIZE DETERMINATION

This is a Phase Ib/II, multicenter study that will enroll up to 18 subjects in Phase Ib and 30 subjects in Phase II of the study. The sample size for Phase Ib is based on conventional 3+3 study design and Phase II is based on clinical judgment. No statistical power calculation is used to establish the sample size.

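### SAP 8.2.2 censors PFS at the start of new anticancer therapy without exempting patients who already have documented progression, in conflict with its own event definition and its next paragraph

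*SAP*

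**What the plan says.** The Phase II primary endpoint is PFS, measured from first treatment "to the date of disease progression or death from any cause, whichever comes first" (SAP 2.4.1). SAP 8.2.2 repeats this: "PFS will be calculated from the date of initial dose to the date of objective disease progression or death due to any cause".

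SAP 8.2.2 then gives two rules for new therapy:

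- At the end of the first paragraph: "Patients will be explicitly censored for PFS at last adequate tumor assessment prior to initiation of new anticancer treatment or radiation".
- In the next paragraph, for "Patients who are off-treatment without objective PD and getting the subsequent new anticancer therapy before the data cut-off": censoring at the last adequate assessment before the new treatment, whatever progression or death comes afterwards.

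The analysis is descriptive: "Progression free survival (PFS) will be estimated using Kaplan-Meier curves, and the median PFS will be read from this curve". The design is a single arm of 30 patients, and SAP 2.1 gives a reference value: "PFS in patients with newly recurred TNBC is approximately 5 months". SAP 7.4 plans no sensitivity analysis. The Protocol has no PFS censoring rule and leaves detailed methods to the SAP (Protocol 8 and 8.7).

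**The concern.** The unqualified sentence applies to all patients who start new anticancer treatment or radiation. Other rules in the same section do state a condition. The rule on discontinuation for toxicity or withdrawal of consent is tied to absence of progression or death, and the next paragraph to absence of objective progression. This sentence has no such limit.

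The situation is an ordinary one. Study treatment normally stops at progression (SAP 2.1), and later anticancer treatments are recorded at survival follow-up (Protocol 4.4.2). The data that would trigger the literal rule will therefore exist for patients who have progressed.

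The median PFS of a small single arm is at stake, and it will naturally be read against the 5-month reference. The error would run in the favourable direction, and no planned analysis would expose it.

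**Working it through.** **Textual check.** Take an illustrative patient with first dose on Day 1, progression on the Day 83 scan and next-line therapy from Day 97.

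| Text in SAP 8.2.2 | Result for this patient |
|---|---|
| Event definition | Event, Day 83 |
| Unqualified new-therapy sentence | Censored at the last adequate scan before Day 97, which is the Day 83 scan |
| Next paragraph | Does not apply, because she has objective progression |

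The date is the same but the status differs. No sentence says which text governs.

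**Size if the literal rule were programmed.** The plan has no figure to reproduce: it states no expected event count or censoring rate, and says "No statistical power calculation is used to establish the sample size".

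Inputs from the documents: N = 30; scans every 6 weeks to week 18, then every 9 weeks; the 5-month reference, used here as the true median.

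Assumptions not in the documents: exponential PFS; progression makes up a share q = 0.9 of PFS events, the rest being deaths; data cut 24 months after first dose; a share f of progressors starts a next line before the cut.

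*Closed form.* Censoring a share f of progressors at their progression date leaves a fraction (1 − f·q) of the hazard, so the apparent median is 5/(1 − f·q) months:

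- f = 0.3: 5/0.73 = 6.8 months
- f = 0.5: 5/0.55 = 9.1 months
- f = 0.7: 5/0.37 = 13.5 months
- f = 0.9: 5/0.19 = 26.3 months

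*Simulation.* 2,000 trials, with progression dated at the next scheduled scan (1 month = 4.348 weeks). The median column is the median of the trial medians.

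| f | PFS events | Kaplan-Meier median | Median not reached |
|---|---|---|---|
| Progression kept as event, any f | 28.8 | 6.2 months (27 weeks) | 0% |
| 0.3, literal | 20.9 | 8.3 months (36 weeks) | 0% |
| 0.5, literal | 15.8 | 10.4 months (45 weeks) | 1% |
| 0.7, literal | 10.7 | 15.8 months (about 69 weeks) | 19% |
| 0.9, literal | 5.5 | not reached | 71% |

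The conventional result of 27 weeks exceeds the true 5 × 4.348 = 21.7 weeks because progression is dated at scans, and 21.7 falls between the scans at weeks 18 and 27. At f = 0.7 the typical median lies between the scans at weeks 63 and 72, and small differences in the simulation move it within that interval. The event counts agree with 28.8 × (1 − f·q): 21.0, 15.8, 10.7 and 5.5.

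The not-reached rates depend on the data cut. With no cut they fall to roughly 10% at f = 0.7 and 55% at f = 0.9.

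**The case against.** The strongest reply is that this is loose drafting which the context repairs. The event definition comes first, so a patient who progressed on Day 83 has already reached her endpoint, and censoring rules ordinarily apply only to patients with no earlier event. The next paragraph states the condition and separates progression before new therapy from progression after it. This carries weight: the conventional rule is probably what was meant. A reader might infer that the SAP intends to censor progressors, and the documents do not support that.

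A reader might also infer that, because the next paragraph handles patients without progression, the unqualified sentence must exist for those with it. That does not follow. Only this sentence mentions radiation, and only this sentence reaches patients still on study treatment who receive other anticancer therapy. Both are prohibited during treatment (Protocol 7.5.2), so a censoring rule for them makes sense. The same fact means that a programmer cannot discard the sentence as a duplicate.

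It is also fair to say that there is no formal hypothesis test (SAP 5), that no decision threshold is tied to the median, and that a progression date flagged as censored could be noticed against the efficacy listings (SAP 12.1). These points limit the consequences. They do not settle which rule applies, and the listings help only if someone makes the comparison.

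**Conclusion.** The point holds as an unreconciled conflict within SAP 8.2.2. One sentence, followed as written, gives the wrong status to a progressor who goes on to a next line. The rest of the section points the other way, but nothing states that progression before new therapy stays an event.

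If the literal rule were used, the bias would be upward and material: 27 weeks would become 36 weeks at a 30% next-line share and 45 weeks at 50%. This rests on the assumptions listed above, chiefly the share of progressors starting a next line, which the documents do not give. The results at 70% and above also have few events, and their not-reached rates depend on the cut.

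A reader might go further and conclude that most primary-endpoint events would vanish. That is true only at high shares. At 50%, 15.8 of 28.8 events remain; fewer than half remain only when 1 − 0.9f < 0.5, that is, f above about 0.56.

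**What to change.** Replace the two new-therapy rules in SAP 8.2.2 with one:

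*Patients with no documented objective PD or death before the start of new anticancer treatment or radiation will be censored at the last adequate tumor assessment before that start, regardless of later PD or death. Objective PD or death documented before that start is a PFS event on its date, subject to the missed-assessment rule in this section.*

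This keeps the cover for radiation and for therapy given during study treatment, and removes the conflict. It should be done before the PFS programs are written, and in any case before database lock. The cost is a short text edit, with no change to design, sample size or data collection.
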